OSU Study #: OSU-13128
IRB Protocol #: 2013C0180
Version: Amd 6 - 01/26/2016
IRB Approved: 04/29/16

**Phase I/II Study of Lenalidomide in Combination with Monoclonal Antibody
MDV9300 (CT-011) in Patients with Relapsed/Refractory Multiple Myeloma**

Clinical Lead (PI): **[name].**
E-mail: [contact]

Scientific Lead: **[name] M.D. Ph.D.**
Email: [contact]

Clinical Site PI: **[name]**
Beth Israel Deaconess
Medical Center Email: [contact]

Clinical Site PI: **[name]**
Dana Farber Cancer
Cancer Institute Email: [contact]

Study Sponsor: **[name]** (Investigator-Sponsor)

IND# 120501

Funding Entity: American Cancer Society

Drug Supplied: MDV9300 by Medivation

Subsite Coordinator: 

Initial: 04Feb2014
Amd 2: 19Feb2014
Amd 3: 26Mar2014
Amd 4: 11Jun2014
Amd 5: 19Jun2015
Amd 6: 26Jan2016

PROTOCOL SYNOPSIS

Study Title	Phase I/II Study of Lenalidomide in Combination with Monoclonal Antibody MDV9300 (CT-011) in Patients with Relapsed/Refractory Multiple Myeloma
Study ID	OSU-13128
Sponsor	[name] (Investigator Sponsor)
IND#	120501
Funding Entity	American Cancer Society
Primary Objectives	To determine the maximum tolerated dose (MTD), safety and efficacy of CT-011 in combination with lenalidomide (Revlimid) and assess efficacy in terms of overall response rate in patients with relapse/refractory multiple myeloma (MM)
Primary Endpoint	
 • To determine MTD of CT-011 in combination with lenalidomide in the phase I study. The MTD of CT-011 combined with lenalidomide will be defined as the highest dose combination of CT-011 and lenalidomide at which ≤ 1 of 6 patients at that dose level has dose-limiting toxicity. • To determine the overall response rate (ORR) after 4 cycles and then at 8 and 12 months in responding patients according to the International Myeloma Working Group (IMWG) response criteria in the phase II study.
Secondary Endpoints	
 • To determine time to progression (TTP) • To determine overall survival (OS) • To assess pharmacokinetics and pharmacodynamics of CT-011 in combination with lenalidomide • To assess CT-011 immunogenicity and correlative biologic studies to assess immunomonitoring of lymphocytes subsets including T and NK cell, and ex-vivo assessment of immune functional activities.
Safety parameters	Infusion related and treatment emergent toxicities per National Cancer Institute Common Terminology Criteria for Adverse Events (NCI CTCAE) v4.0
Study Design	
For the phase I portion
 
We will conduct a standard 3+3 design over 4 dose levels of 1.5, 3, 3, and 6 mg/kg of CT-011 given intravenously every 4 weeks and lenalidomide given at 15, 15, 25, and 25 mg orally daily on days 1-21 of a 28-day cycle.
 
CT-011 will be administered intravenously on day 3 of each 28 day cycle. The drug is diluted into a 250mL saline bag which in the FIRST infusion is administered in a step-wise manner: 50ml/hr for 30min; 100ml/hr for 30min; 150ml/hr for 30 min and 200ml/hr till the end (another ~30min) for an approximate time of 2hrs. If no infusion related AEs occurs the first time, subsequent administrations are at 200mL/hr which will deliver the drug over approximately 1:15hrs. All patients will receive pre-medication (Tylenol 650mg or Ibuprofen 800mg or related medication), and an antihistamine (phenergan 25mg or equivalent) before CT-011 infusion.
 
Patients will be assessed for response at the end of each cycle according to the IMWG response criteria.

Patients will be monitored for safety by assessing toxicities as graded by the NCI CTCAE v4.0. Dose limiting toxicity (DLT) will be defined as one or more of the following toxicities considered to be at least possibly related to one of the study drugs during Cycle 1

- Grade 3 or greater non-hematologic toxicity with the exception of Grade 3 nausea, vomiting and diarrhea that responds to supportive therapy.
- Grade 4 thrombocytopenia, or grade 3 thrombocytopenia with bleeding, or any requirement for platelets transfusion
- Grade 4 neutropenia persisting for more than 5 days.
- Grade 3 or greater febrile neutropenia (temperature $\geq 38.5^{\circ}\text{C}$)
- Grade 4 anemia, unexplained by underlying disease

Patients that experience a lenalidomide-related hematologic DLT may continue on therapy if the event resolves, the investigator considers it in the best interest of the patient to continue and the patient qualifies for initiation of the next cycle with standard of care lenalidomide dose reduction. However, the DLT will count towards establishment of maximally tolerated dose (MTD). A cohort will be expanded if 1 of 3 pts experiences a DLT. If 2 of 6 pts on a cohort experience a DLT, then MTD will be determined as the dose level immediately below that in which 2 of 6 pts experience a DLT. The Phase II portion of the trial will commence upon completion of the Phase I portion. In the event that a MTD is not established, safety and tolerability data collected in the Phase I portion of the study will guide decisions on dosing of CT-011 in the phase II trial.

The maximum tolerated dose level (MTD) combination is defined as the dose level at which no more than one of six patients experiences a DLT as defined above. Any dose level that has two or more DLTs reported is considered to exceed the MTD and not be a tolerable dose level. Dose escalation will be determined based on the occurrence of DLTs observed in the first cycle of therapy. For the purposes of dose determination, DLTs will be counted by patient, i.e., a patient who experiences more than one DLT will be counted only once.

Discontinuation of treatment due to disease progression will not constitute a DLT. In the phase I portion of this trial, if a patient goes off treatment before completing cycle one for reasons other than toxicity or DLT, they will be replaced at that dose level to fully evaluate the tolerability of this regimen at that dose level.

After 4 cycles of therapy or earlier if clinically indicated, response determination will be assessed by the IMWG criteria. At the end of Cycle 4, if a subject has responded (complete or partial response) or has stable disease, dosing with CT-011 and lenalidomide will continue for a minimum of 8 additional cycles or until withdrawal.

If disease progression is observed at the end of Cycle 4 evaluation, all study therapy will be discontinued. Confirmation of progression of disease will be done according to the IMWG criteria.

Following the 30-day post-treatment follow-up assessment, additional evaluations will occur once per month (unless subject discontinued due to progression) until

the earliest of the following events: disease progression, the time of initiation of new therapy, death or study completion.

Study completion is defined as 30 days after the last subject remaining on study medication discontinues study medication.

For the Phase II portion

Upon completion of the cohorts in phase I, the phase II portion of the study will commence utilizing the planned target doses (or MTDs determined) with CT-011 in combination with lenalidomide and dexamethasone

During the phase II portion of this trial, we will not evaluate patients for DLTs as was done in the phase I portion; however, we will use the DLT criteria to identify potential toxicity and tolerability concerns occurring at any cycle to initiate further evaluation to ensure safety of patients. An independent Data Monitoring Committee will continue oversight of this trial.

Treatment will continue until Progression of disease, death, unacceptable toxicity or patient or treating physician decision to discontinue therapy.

Dosing Regimen

Dosing cohorts for the phase I study: We will conduct a standard 3+3 design over 4 dose levels of 1.5, 3, 3, and 6 mg/kg of CT-011 given intravenously every 4 weeks (28 days) on day 3, and lenalidomide given at 15, 15, 25, and 25 mg orally daily on days 1-21 of a 28-day cycle. The study drug CT-011 and lenalidomide can move independently of one another as described in the Table below. Dexamethasone 40 mg orally weekly may be added if only stable disease after 3 cycles according to the IMWG response criteria (section 13-0). Dexamethasone can be reduced to 20 mg based on tolerability or if patient is 70 years or older.

A minimum of 3 patients to a cohort with at least one week break between cohorts.

	CT-011- mg/kg day 3
Cohort -1	1.5
Cohort -2	1.5
Cohort 1	1.5
Cohort 2	3
Cohort 3	3
Cohort 4	6

	Lenalidomide- mg Days 1-21
Cohort -1	10
Cohort -2	5
Cohort 1	15
Cohort 2	15
Cohort 3	25
Cohort 4	25

If a DLT occurs in 2 or more patients during the first cycle, we will consider this

dose level to exceed the MTD and therefore be deemed intolerable for this patient population. If a DLT occurs in 1 of 3 patients during this time, an additional 3 patients will be enrolled and evaluated for DLT before dose escalation can proceed. If no other patient in the cohort has a DLT, escalation to the next cohort may proceed 1 week later from the last included patient on the current cohort. If a second patient in a cohort has a DLT, MTD determination will then be conducted by one of the following schemes:

- If ≥ 2 of 3 patients in cohort 1 exhibit a DLT at the dose of 1.5 mg/kg CT-011 in combination with lenalidomide 15 mg, 3 more patients will be enrolled at a de-escalated dose level cohort. This de-escalation cohort (Cohort -1) will use the same dose of CT-011 (1.5 mg/kg) in combination with 10 mg lenalidomide. If no further DLTs are observed, we will consider dose escalation of the CT-011 with this lower dose of lenalidomide such that the dose escalation of CT-011 to 3 mg/kg with lenalidomide 10 mg will proceed in the next cohort. However, if ≥ 2 patients experience DLT with CT-011 1.5 mg/kg and lenalidomide 10 mg, then we will further de-escalate lenalidomide to 5 mg and enroll 3 more patients on CT-011 1.5 mg/kg combined with lenalidomide 5 mg. The same criteria for MTD will be used for these de-escalation dose level cohorts.
- If ≥ 2 patients in cohort 2 exhibit a DLT at the dose of 3 mg/kg CT-011 in combination with lenalidomide 15 mg, we will explore tolerability of an intermediate dose level of lenalidomide, where 3 patients will be enrolled and treated with 3 mg/kg of CT-011 in combination with 10 mg lenalidomide. The dose escalation of CT-011 to 6 mg/kg with lenalidomide 10 mg will proceed in the next cohort if no more than one DLT is observed in the 3 mg/kg CT-011+10mg lenalidomide cohort.
- If ≥ 2 patients in cohort 3 exhibit a DLT at the dose of 3 mg/kg CT-011 in combination with lenalidomide 25 mg, 3 more patients will be enrolled at the 3 mg dose of CT-011 in combination with 15 mg lenalidomide. If there is < 1 DLT with CT011 3mg/kg and lenalidomide 15 mg, this will be defined as the MTD. If there are 2 or more DLT, then 3 additional patients will be enrolled at the CT-011 3mg/kg and lenalidomide 10 mg, which will become the MTD.
- If ≥ 2 patients in cohort 4 exhibit a DLT at the dose of 6 mg/kg CT-011 in combination with lenalidomide 25 mg, 3 more patients will be enrolled at the 6 mg dose of CT-011 in combination with 15 mg lenalidomide. If there is < 1 DLT with CT011 6mg/kg and lenalidomide 15 mg, this will be defined as the MTD. If there are 2 or more DLT, then 3 additional patients will be enrolled at the CT-011 6mg/kg and lenalidomide 10 mg, which will become the MTD.

Once the MTD has been established or determined, an additional 18 subjects will be treated at the MTD in the phase II.

Planned Sample size	For the phase I portion: a minimum of 12 and a maximum of 30 patients will be recruited. For the phase II portion: a maximum of 23 patients will be recruited
----------------------------	--

Duration of Study Period	
Patient will continue study treatment at the treating physician's discretion
 
Patients achieving at least a stable disease can continue treatment until progression of disease, death, unacceptable toxicity, or patient decision. Overall response will be assessed after 4, 8, and 12 cycles.
 
The total study enrollment period is expected to be up to 12-24 months.

Eligibility	
Inclusion criteria
 
 • Patients must be at least 18 years of age with evidence of relapse or refractory disease as defined by IMWG criteria and measurable disease as defined by any of the following: 
 ○ Serum M-protein ≥ 0.5 g/dl (≥ 10 g/l) ○ Urine monoclonal protein ≥ 200 mg/24h ○ Involved FLC level ≥ 10 mg/dl (≥ 100 mg/l) and an abnormal serum free light chain ratio (<0.26, or >1.65) ○ Measurable biopsy proven plasmacytoma (should be measured within 28 days of registration to study) • Patients must have had at least 2 prior lines of therapy. • Patients must not have had progression of disease on lenalidomide 25 mg. Stable disease on lenalidomide is permitted. • Patient may be enrolled at any time from last line of therapy • Patients must have ANC $> 1000/\mu\text{L}$; Platelets $\geq 75,000/\mu\text{L}$, If plasma cell percentage on bone marrow biopsy aspirate or core is $> 30\%$, platelet eligibility requirement will be adjusted to 60,000/μl. • Patients must have adequate hepatic function as evidenced by: total bilirubin ≤ 1.5 mg/dL, alkaline phosphatase $\leq 3X$ the ULN, AST/ALT $\leq 2X$ the ULN • Patients must have adequate renal function as evidenced by serum creatinine ≤ 2 mg/dL or calculated creatinine clearance of ≥ 40 ml/min within 14 days of registration using MDRD formula. • Patient must be able to swallow capsule or tablet. • Patients must provide informed consent. • Patients must have a left ventricular ejection fraction $> 30\%$, no uncontrolled arrhythmias or New York Heart Association class III-IV heart failure. • Patients must have a Karnofsky performance status ≥ 70. • A negative pregnancy test will be required for all women of child bearing potential. Breast feeding is not permitted. • Fertility requirements 
 ○ Female patients with child bearing potential must have a negative pregnancy test at least 7 days before starting treatment drugs. ○ Male patients must agree to use an adequate method of contraception for the duration of the study and for 90 days afterwards. ○ Female patients must be either post-menopausal, free from menses ≥ 2 yrs, surgically sterilized, willing to use two adequate barrier methods of contraception to prevent pregnancy, or agree to abstain from sexual activity starting from screening and for 90 days afterwards. ○ Female patients of child bearing potential must agree to comply with the fertility and pregnancy test requirements dictated by the Rev-Assist

program.

Exclusion Criteria

- Patients with peripheral neuropathy > CTCAE grade 2
- Patients receiving concurrent corticosteroids other than for physiologic maintenance treatment. Patients should otherwise discontinue corticosteroids prior to registration to study.
- History of allergic reaction (including erythema nodosum) to lenalidomide
- Concurrent use of complementary or alternative medicines that would confound the interpretation of toxicities and antitumor activity of the study drugs.
- Patients with contraindication to thromboprophylaxis
- Unacceptable cardiac risk factors defined by any of the following criteria: Patients with congenital long QT syndrome, any history of ventricular fibrillation or torsade de pointes, bradycardia defined as HR< 50 bpm, Left ventricular ejection fraction < 30%
- Patients who have received targeted or investigational agents prior to registration within 2 weeks or within 5 half-lives of the agent and active metabolites (whichever is longer) and who have not recovered from side effects of those therapies.
- Patients who have undergone major surgery ≤ 2 weeks prior to registration to study or who have not recovered from the side-effects of surgery
- Patients with known positivity for human immunodeficiency virus (HIV), or hepatitis C. Baseline testing for HIV and hepatitis C is not required
- Patients with a history of another primary malignancy that is currently clinically significant or currently requires active intervention, other than non-melanoma skin cancer and carcinoma in situ of the cervix should not be enrolled. Patients are not considered to have a “currently active” malignancy if they have completed therapy for a prior malignancy, are disease free from a prior malignancy for ≥ 5 yrs and are considered by their physician to be less than 30% risk of relapse.
- Patients with active (untreated or relapsed) CNS metastasis of the patient's myeloma.
- Patients with a history of gastrointestinal surgery or other procedure that might, in the opinion of the investigator(s), interfere with the absorption or swallowing of the study drugs.
- Patients with any significant history of non-compliance to medical regimens or unwilling or unable to comply with the instructions given to them by the study staff.

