2 STUDY OVERVIEW AND OBJECTIVE

2.1 Study Overview

This is a single-arm, open label, phase I/II study of CT-011 in combination with lenalidomide in adult (age 18 years and older) patients with relapsed MM. A 4-cohort, dose-escalation, phase I portion will

be completed with the primary endpoint to determine safety and tolerability, seeking maximally tolerated doses (MTDs) of each agent in combination in a standard 3+3 design over 4 dose levels of 1.5, 3, 3, and 6 mg/kg of CT-011 given intravenously every 4 weeks (every 28 days), and lenalidomide given at 15, 15, 25, and 25 mg orally daily on days 1-21 of a 28-day cycle. A minimum of 12 and a maximum of 30 patients will be recruited for the phase I portion of the study. Upon identification of the MTD for the dose level combination of CT-011 and lenalidomide, the phase II portion of the study will commence accruing an additional 23 patients to assess the primary endpoint of overall response rate after 4 cycles by the IMWG criteria. Secondary endpoints include assessment of overall response rate after 8 and 12 cycles of therapy, progression-free survival, pharmacokinetic and pharmacodynamics data, immunomonitoring of lymphocyte subsets, including T and NK cell subsets, and *ex vivo* immune functional assays. For both phases, Dexamethasone 40 mg orally weekly may be added if only stable disease after 3 cycles. Dexamethasone can be reduced to 20 mg based on tolerability or if patient is 70 years or older.

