4.5 Study Accrual

For the phase I portion, a minimum of 12 and a maximum of 30 patients will be recruited. Once the MTD has been established, an additional 23 subjects will be treated at the MTD in the phase II.

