5 TREATMENT PLAN AND PROCEDURES

For the Phase I portion, this is a standard 3+3 design over 4 dose levels of 1.5, 3, 3, and 6 mg/kg of CT-011 given intravenously every 4 weeks (every 28 days) on day 3, and lenalidomide given at 15, 15, 25, and 25 mg orally daily on days 1-21 of a 28-day cycle. The study drug CT-011 and lenalidomide can be escalated or de-escalated independently of one another as described in the Table below. Twelve to 30 patients will be recruited in the phase I portion of the trial. The phase II portion will utilize the 6 patients treated at the MTD in the phase I portion and an additional 23 patients will be accrued. Dexamethasone 40 mg orally weekly may be added if only stable disease after 3 cycles according to the IMWG response criteria (section 13-0). Dexamethasone can be reduced to 20 mg based on tolerability or if patient is 70 years or older.

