Previous studies of lenalidomide alone in a similarly defined relapsed/refractory MM patient population has shown an overall response rate of 25%, which also included the addition of dexamethasone after 2 cycles to non-responding stable disease patients. We will consider this regimen promising if the true overall response rate is 50% or greater when lenalidomide is combined upfront with CT-011. Therefore, we will test the null hypothesis that the true overall response rate (ORR) is at most 25% (reflecting a combination regimen ORR that would not be of interest) versus our alternative hypothesis that the true ORR in patients treated with this combination regimen is at least 50%.

Decision Rule: The largest response rate where this treatment regimen would be considered ineffective in this population is 25%, and the smallest response rate that would warrant subsequent studies with this proposed regimen in this patient population is 50%. The following Three-Outcome phase II study design is a modification of the standard one-stage phase II design and uses a maximum of 29 evaluable patients to test the null hypothesis that the true response rate is at most 25%. Since we will include the 6 patients treated at the MTD from the phase I portion of the trial, this will require accruing an additional 23 evaluable patients for this phase of the study. Based on this study design, there are three possible outcomes:

- **Not promising**: This regimen will be classified as not promising with respect to the response rate in this patient population if at most 9 patients have any response after 4 cycles of therapy out of the total 29 evaluable patients.
- **Promising**: This regimen will be classified as promising with respect to increasing the response rate in this patient population if at least 12 patients have an observed response to treatment after 4 cycles of therapy out of the total 29 evaluable patients. Subsequent larger confirmatory studies may be warranted.

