- **Inconclusive**: The results of this study will be classified as inconclusive with respect to this regimen demonstrating an improved response rate if only 10 or 11 of the 29 total evaluable patients have a response after 4 cycles of therapy. In this case, other factors such as progression-free survival, toxicity, and correlative outcomes will be used in addition to the response data to make the final determination as to whether or not this treatment is considered promising and worthy of further study in this patient population.

In this type of three-outcome phase II design with an uncertainty region, the associated errors are not the same as in the standard phase II study designs. In this study, the type I and type II error rates are constrained at 4% and 3%, respectively; The other parameters included in this type of design are eta (the probability of determining that a regimen is not worth pursuing further when it truly is not effective) and pi (the probability of determining that a regimen is promising when it truly is). Under this design, eta=0.83 and pi=0.87.

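### The 9/12 decision rule has its stated error rates only at a total of 29 patients, and the protocol does not consistently deliver 29

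*Combined protocol and SAP*

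**What the plan says.** **The rule.** Section 6.1.2 describes a one-stage three-outcome design that "uses a maximum of 29 evaluable patients to test the null hypothesis" of a response rate of at most 25%, against an alternative of at least 50%. At most 9 responders is not promising, 10 or 11 is inconclusive, and at least 12 is promising. It adds that "the type I and type II error rates are constrained at 4% and 3%, respectively", with eta 0.83 and pi 0.87.

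**The new patients.** The synopsis (Dosing Regimen) says "an additional 18 subjects will be treated at the MTD in the phase II". The next synopsis row (Planned Sample size) says "For the phase II portion: a maximum of 23 patients will be recruited". Section 2.1 says "the phase II portion of the study will commence accruing an additional 23 patients". Section 4.5 repeats the synopsis sentence with the other number: "an additional 23 subjects will be treated at the MTD in the phase II". Sections 5 and 6.1.2 also give 23.

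**The carried-over patients.** Section 5 says that phase II will "utilize the 6 patients treated at the MTD in the phase I portion and an additional 23 patients will be accrued". Section 6.1.2 reaches 23 by the same route: "Since we will include the 6 patients treated at the MTD from the phase I portion of the trial". This fits the MTD definition in the synopsis and Sections 2.3 and 6.1.1 (at most one DLT in six patients).

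**Replacement and denominator.** Section 5.7 rules out replacing phase II withdrawals. Section 10.7, which is not limited by phase, allows replacement of patients who stop for reasons other than toxicity. The denominator is evaluable patients in the decision rule, eligible treated patients later in Section 6.1.2, and per-protocol patients in Section 6.3. I found no definition of the last.

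**The concern.** The cut-offs are fixed counts, so the primary conclusion has its stated error rates only if the analysed total is 29. Three things can move the total: the number of new patients, the number carried over from phase I, and the handling of early stoppers. On each, the protocol either contradicts itself or leaves a gap. It gives no rule for applying 9/12 at another total.

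A shortfall costs power: an active regimen is more often called not promising or inconclusive. An excess raises the chance of calling an inactive regimen promising. The trial is open-label and phase I responses come first. If nobody has written down which phase I patients count, that choice would be made with their responses in view.

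**Working it through.** **Inputs (Section 6.1.2).** p0 = 0.25, p1 = 0.50, lower cut-off 9, upper cut-off 12, n = 29.

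**Formulas (exact binomial).** Type I = P(X ≥ 12 | n, 0.25). Type II = P(X ≤ 9 | n, 0.50). Eta = P(X ≤ 9 | n, 0.25). Pi = P(X ≥ 12 | n, 0.50).

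**The plan's own figures.** At n = 29 these are 0.0390, 0.0307, 0.8337 and 0.8675, which round to the stated 4%, 3%, 0.83 and 0.87. No other n from 18 to 35 gives this set. At n = 29, no other pair from lower cut-offs 8 to 10 and upper cut-offs 11 to 13 does either.

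**Where the steps leave six open.** Sections 4.3 and 6.1.1 expand a level from three to six only after one DLT in three. Four paths then depart from six:

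- If cohort 4 fails, three patients at a new combination can be named the MTD. The same holds at the last step after cohort 3 fails.
- If the top level is cleared at 0/3, no expansion is stated.
- If cohort 2 was expanded to six and cleared, and cohort 3 then fails, three more are treated at the cohort 2 combination: 6 + 3 = 9.
- The synopsis and Section 4.3 foresee that no MTD is established. Then nobody was treated at the MTD, and Section 6.1.2 does not say who is counted.

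**Same cut-offs at other totals:**

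| Case | n | Type I | Type II | Eta | Pi |
|---|---|---|---|---|---|
| None carried over + 23 | 23 | 0.5% | 20.2% | 0.96 | 0.50 |
| Six + 18 (synopsis sentence) | 24 | 0.7% | 15.4% | 0.95 | 0.58 |
| Three + 23 | 26 | 1.5% | 8.4% | 0.91 | 0.72 |
| Six + 23, one not evaluable | 28 | 2.9% | 4.4% | 0.86 | 0.83 |
| Six + 23 (as planned) | 29 | 3.9% | 3.1% | 0.83 | 0.87 |
| Six + 23, one replaced, both counted | 30 | 5.1% | 2.1% | 0.80 | 0.90 |
| Nine + 23 | 32 | 8.0% | 1.0% | 0.74 | 0.94 |

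**Early stoppers.** If Section 5.7 governs and all eligible treated patients are counted, an early stopper stays in as a non-responder and n is still 29. If only evaluable patients count, one loss gives n = 28. If one of 30 treated patients stops without response and is replaced, and the 25% null is taken to apply to all treated patients, the rate among the 29 evaluable is 0.25 × 30/29 = 0.2586. Then P(X ≥ 12 | 29, 0.2586) = 0.0496, about 5.0%. If the 25% null applies to the evaluable patients themselves, type I error stays at 3.9%.

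**The case against.** The strongest reply is that the intended design is clear. Section 6.1.2 sets out 6 + 23 = 29 in full and its arithmetic is correct. Five places give 23, and Section 4.5 has the synopsis sentence with 23 in it. The MTD definition requires six patients, so a top level cleared at 0/3 does not meet it until expanded. Section 5.7 is specific to phase II and should prevail over the general, permissive text of Section 10.7. Section 6.1.2 itself names the primary denominator.

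Most of this stands, and it rules out three stronger readings that a reader might infer:

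- *The trial is sized at 24 and underpowered.* One sentence against five, and against the design section, does not support this.
- *Replacement inflates type I error in any case.* It does so only if the replaced patient is also counted, which would breach the maximum of 29 in Section 6.1.2 and of 23 in the synopsis, or if the 25% null covers all treated patients. Section 6.1.2 frames the test on 29 evaluable patients.
- *A total of 26 is the likely outcome.* The frequency of each path depends on DLT rates for this combination, which the documents do not give. It also requires that the three patients are carried over and the level is not expanded.

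The reply does not remove the gap between the six-patient definition and the steps that can name an MTD on three or leave nine at one dose. It does not say who counts when no MTD is established. The conflicts between Sections 5.7 and 10.7, and between Sections 6.1.2 and 6.3, also remain.

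**Conclusion.** This is an internal inconsistency that should be fixed, not a calculation error. The 9/12 rule is correct for 29 patients, and the text around it does not reliably produce 29.

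The wrong synopsis figure is very probably editorial. The substantive gap is the number carried over. With 23 new patients, type II error ranges from 20.2% (none) to 1.0% (nine), and type I error from 0.5% to 8.0%. One non-evaluable patient is a smaller matter: type II error 4.4% and pi 0.83.

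These sizes assume independent responses at the protocol's own 25% and 50%, unchanged cut-offs and 23 new patients. They say what happens in each case, not how often each case arises.

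**What to change.** 1. In the synopsis (Dosing Regimen), change 18 to 23.
2. Reconcile the six-patient MTD definition with the dose-finding steps in the synopsis and Sections 4.3 and 6.1.1. Which of them should govern is for the sponsor to decide. In Section 6.1.2, state which phase I patients are counted when the number at the phase II dose is not exactly six, or when no MTD is established.
3. Make Section 10.7 agree with Section 5.7 for treated phase II patients.
4. Use the eligible-treated denominator of Section 6.1.2 in the decision rule and in Section 6.3. The response-rate sentence in Section 6.3 also counts stable disease as response, whereas Section 6.1.2 counts only partial and complete responses; reconcile that too.
5. In Section 6.1.2, before the phase II analysis, state the operating characteristics of 9/12 if the analysed total is 23, 26, 28 or 32, as tabulated above. The sponsor's statistician should pre-specify any alternative cut-offs.

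The cost is wording changes in an amendment, and having to state less favourable error rates if the total is not 29.
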